## 9.2.2 Definition - Adverse Event (AE)

Adverse event is defined as any unfavorable and unintended sign (including an abnormal laboratory finding), symptom or disease temporally associated with the use of a medical treatment or procedure regardless of whether it is considered related to the medical treatment or procedure (attribution of unrelated, unlikely, possible, probable, or definite).

## 9.2.3 Relationship

The Investigator will be asked to document his/her opinion of the relationship of the event to study medication as follows:

- *Unrelated*  
The adverse event is clearly not related to the investigational agent(s).
- *Unlikely*  
The adverse event is doubtfully related to the investigational agent(s).
- *Possible*  
The adverse event may be related to the investigational agent(s).
- *Probable*  
The adverse event is most likely related to the investigational agent(s).
- *Definite*  
The adverse event is clearly related to the investigational agent(s).

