### **Reference Group Treatment Plan**

Patients in this group will receive no study medication pre-surgically.

In order to accommodate biological sample collection, **surgery must take place Monday-Thursday**, with the exception of patients being treated at Memorial Sloan-Kettering Cancer Center: these patients may undergo surgery Monday- Friday.

Tumor tissue samples will be acquired during surgery to resect brain tumor. Tumor specimens will be snap frozen for determination of EGFR phosphorylation. Instructions for collecting and handling tumor specimens are in Sections [9.5.1](#) and [9.5.4](#).

Following surgery, patients will continue with standard post-operative management.

After recovery from surgical resection, patients will receive lapatinib post-operatively twice a day for two consecutive days every 7 days (2 days on/5 days off) in 28-day cycles.

Adequate recovery from surgical resection includes, but is not limited to, the following:

- No signs or symptoms of infections related to the surgical wound (*i.e.*, increasing erythema or cellulitis of the surrounding area, large amount of drainage, fever)
- Wound edges have healed

Post-operatively, patients must begin treatment within 30 days of surgical resection, and preferably within 3 weeks of the post-operative MRI; if more than 3 weeks elapse after the post-operative MRI, the patient will need a new MRI.

Patients will be followed by routine blood work, general and neurological examination, and MR imaging. See Section [9.1](#) for schedule.

Patients may continue to receive cycles of lapatinib until tumor progression, development of unacceptable toxicity, or meeting other criteria for going off treatment (Section [10.1](#)). Patients will be followed for adverse events for at least 30 days after the last dose of lapatinib. All patients will be followed for survival.

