## 9.2.4 Recording of Adverse Events - ABTC AE Form

### • Document on ABTC Adverse Event Data Form

- The Investigator will monitor each patient closely for the development of adverse events and record all such events on the ABTC AE Case Report Form. Each single sign or symptom must be reported separately.
- **CTCAE term (AE description) and grade:** The descriptions and grading scales found in the NCI Common Terminology Criteria for Adverse Events (CTCAE) version 5.0 will be utilized for AE reporting. All appropriate treatment areas should have access to a copy of the CTCAE version 5.0. A copy of the CTCAE version 5.0 can be downloaded from the CTEP web site ([http://ctep.cancer.gov/protocolDevelopment/electronic\\_applications/ctc.htm](http://ctep.cancer.gov/protocolDevelopment/electronic_applications/ctc.htm)). **You must use one of the CTCAE criteria to define your event.**
- Adverse events not included in the CTCAE should be reported under “Other” within the appropriate category and graded 1 to 5 according to the general grade definitions - mild, moderate, severe, life-threatening, fatal or disabling - as provided in the CTCAE or the CTCAE Manual. New adverse events may be submitted to the CTEP Help Desk at [[contact]](mailto:[contact]) for annual evaluation by the CTCAE Change Management Committee.
- Abnormal lab results which are graded by NCI CTCAE will be recorded on the ABTC Laboratory Cover Sheet along with documented attribution, not on the AE form. However, if an action was taken due to this abnormality (e.g. RBC transfusion due to low Hgb) this would be recorded on the AE form also.

All adverse events should be followed up in accordance with good medical practice. Abnormalities of laboratory events which, in the opinion of the investigator, constitute adverse events (even if not serious) should be followed.

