Initial safety monitoring: All adverse events will be monitored and collected throughout the trial and documented based on CTCAE version 5.0. If there are three or more delays of scheduled surgery due to lapatinib-related Serious Adverse Events among the initial 8 patients; or if there are any surgical complications and delayed wound healing SAEs grade  $\geq 3$  considered lapatinib-related among the first three patients, ABTC investigators will consult with CTEP investigators and the pharmaceutical sponsor about such events. An internal safety monitoring evaluation will be conducted after the first three patients complete their first follow-up visit after surgery.

Reference Group (for primary PD study):

15 lapatinib-naïve patients with recurrent and surgically accessible EGFR-amplified high-grade glioma will be enrolled as a reference group for the PD evaluation to establish the threshold of 80% reduction in the ratio of pEGFR/total EGFR. After the initial 8 patients are enrolled into Group A, eligible patients will be sequentially assigned to either treatment group or reference group. The sample size of 15 patients on the reference arm yields 90% confidence that the observed median falls between the true 30th and 70th percentiles of the pEGFR/total EGFR distribution for untreated patients.

To avoid batch effect and other variations through tumor sample processing, all tumor samples will be processed at the same time at the [name] Lab, Memorial Sloan-Kettering Cancer Center.

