### **Secondary and Exploratory Objectives:**

1. All treatment or surgically related AEs will be reported descriptively. A proportion of toxicity grade  $\geq 3$  will be estimated using binomial distribution.

2. To estimate inhibition of tumor cell proliferation (KI-67), descriptive statistics will be used for summarizes results and Box plots could be used to present the difference between the treated and untreated groups.
3. To characterize ex-vivo sensitivity of tumor sphere cultures to lapatinib, the *ex-vivo* sensitivity of tumor sphere cultures established from surgical specimens to pulsatile lapatinib is defined by a minimum of 20% reduction in cell proliferation as measured by cell titer glow in the pulsatile lapatinib group compared to the untreated group. Fisher's exact test will be used for testing a difference in the proportion between the two groups.
4. To estimate tumor objective response rate as the evidence of biological activity among patients with recurrent GBM treated by lapatinib, the proportion of patients who had objective PR or CR during the course of the treatment will be estimated along with 95% confidence intervals using the exact binomial method.
5. To estimate overall survival (OS), the survival time is defined from the date of treatment start to the date of death. Patients who have not expired by the data analysis cutoff date will be censored at their last date known to be alive. The Kaplan-Meier method will be used to estimate overall survival probability and median time of survival along with a 95% confidence interval.
6. To estimate progression-free survival, The progression is defined a radiographic tumor progression, a  $\geq 25\%$  increasing from baseline scan with a confirmatory scan at least 8 weeks apart from the initial scan that tumor progression was observed. The date of progression is defined as the date of initial scan deemed tumor progression. The Kaplan-Meier method will be used to estimate progression-free survival probability and median time of survival along with a 95% confidence interval. The progression-free survival at 6-month is defined as: patient, who started treatment, is alive and progression free at the time of 6 month follow-up. The probability of 6-month progression-free survival will be estimated using binomial distribution.

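### Adverse events are rated only against study medication, yet the safety report selects surgically related events and the protocol gives no item or rule that identifies them

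*Combined protocol and SAP*

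**What the plan says.** Section 9.2.3 gives the instruction on attribution: "The Investigator will be asked to document his/her opinion of the relationship of the event to study medication as follows". It lists five levels, from Unrelated to Definite, and words each one in terms of the investigational agent. Surgery is not mentioned.

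Section 11, item 1 of the secondary and exploratory objectives, defines the safety report: "All treatment or surgically related AEs will be reported descriptively". The only numerical summary in that item begins "A proportion of toxicity grade" and concerns grade 3 or higher, estimated as a binomial proportion. No denominator is given.

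Four other places bear on the point:

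- Section 9.2.2, the definition of an adverse event, does mention procedures: "regardless of whether it is considered related to the medical treatment or procedure (attribution of unrelated, unlikely, possible, probable, or definite").
- Section 9.2.4 tells the investigator to "record all such events on the ABTC AE Case Report Form".
- Section 4.1 says of the Reference Group: "Patients in this group will receive no study medication pre-surgically". These patients start lapatinib after recovery, no later than 30 days after resection.
- Section 9.2 restricts toxicity evaluation to patients who have taken lapatinib at least once.

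**The concern.** The safety report selects on two properties, relation to treatment and relation to surgery. The protocol asks the investigator to judge only the first. The set of events for the surgical half of the report is therefore undefined, and the judgement that would define it is not asked for when the event occurs.

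This matters more here than in most early-phase studies. Section 2.2 states that there is no identified experience with pulsatile lapatinib around any surgery and that the wound-healing and infection risk at these doses is unknown. Section 1.0 lists the safety objective under both groups, and the Reference Group has its operation without prior drug. After a craniotomy, headache, seizure or infection may come from the operation, the tumour or the drug. The investigator at the bedside is better placed to judge this than someone sorting listings later.

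**Working it through.** There is no stated figure to reproduce and no arithmetic to run. The check sets the sections side by side.

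1. **What the report needs.** Section 11 item 1 needs two facts for each event: whether it is related to treatment, and whether it is related to surgery.

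2. **What 9.2.3 supplies.** It supplies one rating, against study medication. That answers the first question only. An event that is clearly not drug-related but clearly caused by the craniotomy is rated Unrelated, and so is an event caused by neither.

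3. **Whether another section supplies the second fact.**
   - 9.2.2 names procedures, but it defines what counts as an adverse event; it does not tell the investigator to rate relation to surgery. Section 5.1 points to 9.2.2 when it requires attribution to lapatinib, so the protocol itself reads those levels as drug attribution.
   - 9.2.4 requires term and grade, and attribution for graded laboratory results. It adds no surgical rating.
   - 9.3.3 asks for attribution of deaths to treatment or to something else. It covers deaths only and does not name surgery.
   - No section gives a list of terms or a time window for surgically related events.

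4. **How the scale works in each group.** Take the same wound complication found at the adverse event evaluation due within 3 days after surgery (Section 9.1, both tables).
   - Group A: the fourth lapatinib dose is scheduled for the morning of surgery, so any of the five levels is open.
   - Reference Group: no lapatinib has been taken, so Unrelated is the only level that fits.
   - Once a Reference Group patient starts post-operative lapatinib, all five levels are open again. The asymmetry is confined to events before that first dose, in a group planned at 15 patients (Section 3.1).

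5. **Who is counted.** A Group A patient who completes pre-operative dosing already meets the one-dose rule in 9.2. A Reference Group patient whose surgical complication prevents post-operative lapatinib never meets it. If that rule governs item 1, this patient's surgical event leaves the report. Section 11 does not say whether it does.

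**The case against.** The strongest reply is that nothing is missing from the data. All adverse events are recorded whatever their attribution, with term and grade, so surgical events can be picked out later by term and timing. The adverse event form is not among the documents, so a surgery field on it cannot be ruled out. This stands. A reader might infer that surgically related events cannot be selected at all; the documents do not support that. What they support is that the protocol states no item or rule for selecting them.

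A second reply is that item 1 says treatment or surgery, so an event unrelated to drug but related to surgery belongs in the report. No between-group safety test is planned, and Section 11 describes the Reference Group as serving the pharmacodynamic study. This also stands. A reader might infer that the Reference Group's surgical events would be counted as zero and that lapatinib would look falsely hazardous. That would need selection on drug attribution alone, which item 1 does not state.

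A reader might also infer that the early safety rule in Section 11, covering "any surgical complications and delayed wound healing SAEs grade" 3 or higher, is impaired. It is not. That rule asks whether such events are considered lapatinib-related, which 9.2.3 does record, and it looks at the first three patients, who are all in Group A.

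Finally, the trial is open-label, so a new surgical rating would also be made with the group known. That is true. The gain is a judgement made at the time on a common scale, not a blinded one.

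**Conclusion.** The point holds in a limited form. The protocol asks for relation to study medication only, while its own safety report also selects on relation to surgery, and no section connects the two. Surgical relation would have to be assigned retrospectively. For Reference Group events before the first lapatinib dose, the stated scale gives no help, because only Unrelated is available.

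The documents give no complication rate, target or precision for this summary, so the number of events affected cannot be stated. The consequence is confined to a secondary descriptive safety summary. The primary endpoints, the futility rule and the early safety rule are unaffected. The conclusion rests on the protocol text and assumes that the adverse event form, which is not in the documents, follows 9.2.3. If the form already carries a surgery field, what remains is to describe it in 9.2.3 and define its use in Section 11.

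It is worth correcting because an attribution made at the time of the event cannot be recovered at analysis.

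**What to change.** Make three changes:

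1. In 9.2.3 and on the adverse event form, add a second relationship, to protocol surgery, on the same five levels, in both groups, completed at the time of the event. The existing drug rating stays as it is; Unrelated is a correct drug rating for an event before any drug.
2. In Section 11 item 1, define surgically related as possible, probable or definite on the new field. Section 5.1 already uses that cut for lapatinib-related toxicity.
3. In Section 11 item 1, report surgically related events by group among all patients who had protocol surgery, and say in 9.2 that the one-dose rule does not apply to this report. Reference Group patients who never start lapatinib then stay in the denominator.

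The cost is one extra form field per event and a few sentences in 9.2, 9.2.3 and Section 11. No visits or procedures are added.

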## 9.2.4 Recording of Adverse Events - ABTC AE Form

### • Document on ABTC Adverse Event Data Form

- The Investigator will monitor each patient closely for the development of adverse events and record all such events on the ABTC AE Case Report Form. Each single sign or symptom must be reported separately.
- **CTCAE term (AE description) and grade:** The descriptions and grading scales found in the NCI Common Terminology Criteria for Adverse Events (CTCAE) version 5.0 will be utilized for AE reporting. All appropriate treatment areas should have access to a copy of the CTCAE version 5.0. A copy of the CTCAE version 5.0 can be downloaded from the CTEP web site ([http://ctep.cancer.gov/protocolDevelopment/electronic\\_applications/ctc.htm](http://ctep.cancer.gov/protocolDevelopment/electronic_applications/ctc.htm)). **You must use one of the CTCAE criteria to define your event.**
- Adverse events not included in the CTCAE should be reported under “Other” within the appropriate category and graded 1 to 5 according to the general grade definitions - mild, moderate, severe, life-threatening, fatal or disabling - as provided in the CTCAE or the CTCAE Manual. New adverse events may be submitted to the CTEP Help Desk at [[contact]](mailto:[contact]) for annual evaluation by the CTCAE Change Management Committee.
- Abnormal lab results which are graded by NCI CTCAE will be recorded on the ABTC Laboratory Cover Sheet along with documented attribution, not on the AE form. However, if an action was taken due to this abnormality (e.g. RBC transfusion due to low Hgb) this would be recorded on the AE form also.

All adverse events should be followed up in accordance with good medical practice. Abnormalities of laboratory events which, in the opinion of the investigator, constitute adverse events (even if not serious) should be followed.

## 9.3 Serious Adverse Events and Expedited Adverse Event Reporting

### 9.3.1 Definition – Serious Adverse Event (SAE)

An adverse event is considered serious if it results in ANY of the following outcomes:

- 1) Death
- 2) A life-threatening adverse event

- 3) An adverse event that results in inpatient hospitalization or prolongation of existing hospitalization for  $\geq 24$  hours
- 4) A persistent or significant incapacity or substantial disruption of the ability to conduct normal life functions
- 5) A congenital anomaly/birth defect
- 6) Important Medical Events (IME) that may not result in death, be life threatening, or require hospitalization may be considered serious when, based upon medical judgment, they may jeopardize the patient or subject and may require medical or surgical intervention to prevent one of the outcomes listed in this definition.

### 9.3.2 CTEP Adverse Event Reporting System (CTEP-AERS)

- **Use CTEP-AERS Web Application and Document on ABTC AE Form**

- Expedited AE reporting for this study must use CTEP-AERS (CTEP Adverse Event Reporting System), accessed via the CTEP Web site (<http://ctep.cancer.gov>). The reporting procedures to be followed are presented in the “NCI Guidelines for Investigators: Adverse Event Reporting Requirements” which can be downloaded from the CTEP Web site (<http://ctep.cancer.gov>).
- This study will utilize the descriptions and grading found in the NCI Common Terminology Criteria for Adverse Events (CTCAE) version 5.0 for toxicity and Serious Adverse Event Reporting. A copy of the CTCAE version 5.0 can be downloaded from the CTEP web site (<http://ctep.cancer.gov>). All appropriate treatment areas should have access to a copy of the CTCAE version 5.0. You must use one of the CTCAE criteria to define your event.

Serious Adverse Events not included in the CTCAE should be reported under “Other” within the appropriate category and graded 1 to 5 according to the general grade definitions - mild, moderate, severe, life-threatening, fatal or disabling - as provided in the CTCAE or the CTCAE Manual.

- Use the NCI protocol number and the protocol-specific patient ID provided during trial registration on all reports.
- In the rare occurrence when Internet connectivity is lost, a 24-hour notification is to be made to CTEP by telephone at [contact]. Once Internet connectivity is restored, the 24-hour notification phoned in must be entered electronically into CTEP-AERS by the original submitter at the site.
- CTEP-AERS is programmed for automatic electronic distribution of reports to the following individuals: Study Coordinator of the Lead Organization,

Principal Investigator, and the local treating physician. CTEP-AERS provides a copy feature for other e-mail recipients.

#### Secondary Malignancy:

A secondary malignancy is a cancer caused by treatment for a previous malignancy (e.g., treatment with investigational agent/intervention, radiation or chemotherapy). A secondary malignancy is not considered a metastasis of the initial neoplasm.

CTEP requires all secondary malignancies that occur following treatment with an agent under an NCI IND/IDE be reported via CTEP-AERS. Three options are available to describe the event:

- Leukemia secondary to oncology chemotherapy (e.g., acute myelocytic leukemia [AML])
- Myelodysplastic syndrome (MDS)
- Treatment-related secondary malignancy

Any malignancy possibly related to cancer treatment (including AML/MDS) should also be reported via the routine reporting mechanisms outlined in each protocol.

#### Second Malignancy:

A second malignancy is one unrelated to the treatment of a prior malignancy (and is NOT a metastasis from the initial malignancy). Second malignancies require ONLY routine reporting via CDUS unless otherwise specified.

### 9.3.3 Expedited Reporting Requirements

Note: A death on study requires both routine and expedited reporting regardless of causality, unless as noted below. Attribution to treatment or other cause must be provided.

Death due to progressive disease should be reported as Grade 5 “Disease Progression” in the system organ class (SOC) “General disorders and administration site conditions”. Evidence that the death was a manifestation of underlying disease (e.g., radiological changes suggesting tumor growth or progression: clinical deterioration associated with a disease process) should be submitted.

#### **Phase 1 and Early Phase 2 Studies: Expedited Reporting Requirements for Adverse Events that Occur on Studies under an IND/IDE within 30 Days of the Last Administration of the Investigational Agent/Intervention**

##### **FDA REPORTING REQUIREMENTS FOR SERIOUS ADVERSE EVENTS (21 CFR Part 312)**

**NOTE:** Investigators **MUST** immediately report to the sponsor (NCI) **ANY** Serious Adverse Events, whether or not they are considered related to the investigational agent(s)/intervention (21 CFR 312.64)

An adverse event is considered serious if it results in **ANY** of the following outcomes:

 
1) Death
 
2) A life-threatening adverse event
 
3) An adverse event that results in inpatient hospitalization or prolongation of existing hospitalization for <math>\geq</math> 24 hours
 
4) A persistent or significant incapacity or substantial disruption of the ability to conduct normal life functions
 
5) A congenital anomaly/birth defect.
 
6) Important Medical Events (IME) that may not result in death, be life threatening, or require hospitalization may be considered serious when, based upon medical judgment, they may jeopardize the patient or subject and may require medical or surgical intervention to prevent one of the outcomes listed in this definition. (FDA, 21 CFR 312.32; ICH E2A and ICH E6).
 
		

ALL SERIOUS adverse events that meet the above criteria MUST be immediately reported to the NCI via CTEP-AERS within the timeframes detailed in the table below.
		
Hospitalization	Grade 1 and Grade 2 Timeframes	Grade 3-5 Timeframes
Resulting in Hospitalization $\geq$ 24 hrs	10 Calendar Days	24-Hour 5 Calendar Days
Not resulting in Hospitalization $\geq$ 24 hrs	Not required	

NOTE: Protocol-specific exceptions to expedited reporting of serious adverse events are found in the Specific Protocol Exceptions to Expedited Reporting (SPEER) portion of the CAEPR.
 
Expedited AE reporting timelines are defined as:
 
 
o "24-Hour; 5 Calendar Days" - The AE must initially be reported via CTEP-AERS within 24 hours of learning of the AE, followed by a complete expedited report within 5 calendar days of the initial 24-hour report.
 
o "10 Calendar Days" - A complete expedited report on the AE must be submitted within 10 calendar days of learning of the AE.
 
		

Serious adverse events that occur more than 30 days after the last administration of investigational agent/intervention and have an attribution of possible, probable, or definite require reporting as follows:  Expedited 24-hour notification followed by complete report within 5 calendar days for:
 
 
• All Grade 3, 4, and Grade 5 AEs
 
 
Expedited 10 calendar day reports for:
 
 
• Grade 2 AEs resulting in hospitalization or prolongation of hospitalization
 
 
 For studies using PET or SPECT IND agents, the AE reporting period is limited to 10 radioactive half-lives, rounded UP to the nearest whole day, after the agent/intervention was last administered. Footnote "1" above applies after this reporting period.
		

Effective Date: May 5, 2011
		

